Efficacy and Safety of Catheter Ablation for Atrial Fibrillation in Non-fluoroscopic
Cardiac Electrophysiology Lab:
A Non-Inferior, Multi-Center, Prospective Randomized Controlled Trial
(NCT06719921)

Protocol

Version V3.0

11/27/2025

PROTOCOL SYNOPSIS

Title	Efficacy and Safety of Catheter Ablation for Atrial Fibrillation in Non-Fluoroscopic Cardiac Electrophysiology Lab: A Non-Inferior, Multi-Center, Prospective Randomized Controlled Trial
Purpose	A randomized controlled trial to investigate whether catheter ablation in a non-fluoroscopy lab is non-inferior to catheter ablation in a conventional DSA lab in terms of efficacy and safety for treating atrial fibrillation (AF).
Principal Investigator	[name]
Coordinating Center	Sir Run Run Shaw Hospital serves as the coordinating center for this clinical study with 16 EP centers participating.
Trial Sponsor	Biosense Webster
Number of Subjects	Up to 724 patients (procedures) will be enrolled over 1 year at 16 EP centers.
Inclusion Criteria	
Subjects must meet all the following inclusion criteria to be eligible for participation in this trial.
 
 • Age: ≥ 18 years • Patients diagnosed with paroxysmal AF or persistent AF ≤ 1 year, who are referred for catheter ablation. • Patients referred for catheter ablation of AF (Pulmonary Vein Isolation) as a first-time intervention (no prior catheter ablation or surgical procedures for AF). • The patient is able and willing to provide written informed consent

Exclusion Criteria	
Subjects who meet any of the following exclusion criteria are not eligible for enrollment.
 
 • Patients with contraindication to anticoagulation or to right or left sided cardiac catheterization • Patients scheduled for AF ablation procedures other than PVI and requiring X-ray fluoroscopy, such as VOM ablation, epicardial ablation, LAAO, CAG, etc. • Serious known concomitant disease with a life expectancy of < 1 year • MI, CABG, or PCI within the preceding 3 months • Left atrial diameter >55 mm • LVEF<30% • NYHA class III or IV • Awaiting cardiac transplantation or other cardiac surgery within 12 months. • History of a documented thromboembolic event within the past 6 weeks. • Heart or vascular malformation that impedes catheter access or vascular puncture. • Current enrollment in an investigational study evaluating another device or drug. • Acute illness, active systemic infection, or sepsis. • Significant congenital anomaly or a medical problem that in the opinion of the investigator would preclude enrollment in this trial.
Type	A Non-Inferior, Multi-Center, Prospective Randomized Controlled Trial
Design	Sample Size Justification

1) The sample size calculation will be based on the primary efficacy endpoint.

Sample-size was calculated by non-inferiority log-rank test with 1:1 design. The expected recurrence rate of AF is 30% for control group based on previous studies and our experience, and a hazard ratio of 1.3 was used for establish non-inferiority. Based on a power of 80% and an alpha of 0.05, proportion lost to follow up 5%, **a sample size of 724 patients** (362 for each group) was estimated.

Non-Inferiority Logrank Tests

Numeric Results in Terms of Sample Size

[figure not shown]
Power	N1	N2	N	Equiv			Actual			Ref			Acc-			Ref	Trt	to	Trt	to	Ref	Alp
				Haz	Haz	Haz	Ref	Acc-	Time/	Total	Ref	Trt	Ref	Trt	Trt							
				Ratio	Ratio	Rate	Pat'n	Time	Total	Ref	Trt	Ref	Trt	Trt	Ref	0.0500	0.0500	0.0000	0.0000	0.05		
0.8003	361	362	723	1.30	1.00	0.3000	Equal	1 / 3	0.0500	0.0500	0.0000	0.0000	0.0000	0.0000	0.05							

References

Jung, Sin-Ho; Kang, Sun J.; McCall, Linda M.; Blumenstein, Brent. 2005. 'Sample Sizes Computation for Two-Sample Noninferiority Log-Rank Test', *J. of Biopharmaceutical Statistics*, Volume 15, pages 969-979. Lakatos, Edward. 1988. 'Sample Sizes Based on the Log-Rank Statistic in Complex Clinical Trials', *Biometrika* Volume 44, March, pages 229-241.

2) Safety endpoints will be collected in details and analyzed for comparison between the groups, but they will not be used to determine the sample size.

Flowchart

Ablation Procedure details (study and control group)

The study will target AF catheter ablation procedures (Pulmonary Vein Isolation). After obtaining written informed consent, eligible patients will be randomized into one of the following two groups:

Group 1: Non-Fluoroscopic Lab Group

1. Ablation procedures will be performed in a catheterization lab equipped with non-fluoroscopic 3D electroanatomic mapping systems.
2. No routine fluoroscopy will be used, except if deemed necessary for safety (e.g., complications or unexpected procedural difficulties), adhering to the ALARA principle.
3. Pulmonary vein isolation (PVI) will be the sole ablation strategy, following the study protocol.

Group 2: Fluoroscopic Lab Group (DSA Lab)

1. Ablation procedures will be conducted in a fluoroscopy-guided catheterization lab using digital subtraction angiography (DSA) for catheter navigation.
2. Radiation exposure will be recorded, and efforts will be made to minimize exposure by following the ALARA principle.
3. Similar to Group 1, PVI will be the sole ablation strategy, as per protocol.

Ablation strategy

The primary ablation strategy for both groups will be pulmonary vein isolation (PVI).

Other additional ablation, including but not limited to linear ablation, complex fractionated atrial electrogram (CFAE) ablation, or superior vena cava (SVC) isolation is not recommended unless necessitated by one of the following:

- Documented atrial flutter (AFL) or atrial tachycardia (AT) observed during the procedure, or
- Arrhythmias originating from the specific region requiring intervention.

Energy Selection Principles

Energy modality (RF or PF) will be selected by the investigator prior to randomization according to routine clinical practice, with a population-level expectation that the proportion of PFA among newly enrolled patients will progressively increase to approximately 50–60%, without influencing individual clinical decision-making.

Recommendations

- 1) The configuration of the Non-fluoroscopic Lab needs to be in accordance with the latest expert consensus

	
recommendations (Jiang C, et al. Pacing Clin Electrophysiol. 2023 Sep;46(9):1035-1048).
 
 2) The use of ICE catheter is required for both groups. The application of ICE technology includes but is not limited to: visualizing the cardiac anatomy; guiding catheter placement, transeptal puncture (if necessary); constructing the geometry; monitoring intracardiac thrombus and cardiac effusion throughout the procedure. 3) Magnetic mapping catheters (e.g. Lasso, PentaRay, or DECANAV) is recommended to create the cardiac geometry. 4) A safe, rapid, and smooth plan for transfer to the DSA lab should be established if no mobile DSA equipment is available in the Non-fluoroscopic EP Lab. In the event of an emergency requiring the use of DSA, patient transfer should be completed in a minimal period to maximize patient safety. 5) If deemed necessary, X-ray imaging may be utilized to guide catheter placement and monitor for potential complications. The use of X-ray must adhere to the As Low As Reasonably Achievable (ALARA) principle, ensuring radiation exposure is minimized while maintaining procedural safety and effectiveness.
Duration	April 22, 2025 – April 21, 2028, The study will be completed after the last enrolled subject has finished the 12-month follow-up period.
Objectives	To evaluate the efficacy and safety of AF ablation without the use of fluoroscopy.

Primary endpoint	
 • The primary efficacy endpoint is treatment success at 12 months without AAD, defined as freedom from recurrence of AF/AFL/AT lasting longer than 30 seconds. • The primary safety endpoint is a composite of the following prespecified procedure-related serious adverse events: death, stroke, transient ischemic attack, myocardial infarction, major vascular complication, or major bleeding within the first 7 days post procedure; development of a clinically significant pericardial effusion within 30 days; symptomatic pulmonary vein stenosis, atrial-esophageal fistula, or phrenic nerve injury within 3 months.
Secondary endpoint	
 • The initial success of the procedure. • The proportion of intraoperative conversion to using X-ray. • Utilization of lead personal protective equipment (PPE) and wear time. • Quality-of-life for staff at the end of each procedure. • The proportion of patients with recurrence of AF/AFL/AT during the first 90 days post-ablation. • Early recurrence of atrial arrhythmias, defined as any AF/AFL/AT episode lasting >30 seconds occurring during the blanking period. • Late recurrence of atrial arrhythmias, defined as any documented AF/AFL/AT episode lasting >30 seconds occurring after the blanking period and up to 12 months. • Impact of early recurrence on late recurrence, assessed through survival analysis and multivariable adjustment to evaluate whether early recurrence predicts

	
subsequent late recurrence.
 
 • AF burden, assessed by scheduled rhythm monitoring (e.g., 7-day Holter at 3, 6, 9, and 12 months), expressed as the proportion of time spent in AF during the monitoring period. • Incidence of peri-procedural complication. • Total procedure duration, ablation time. • Changes in quality-of-life
Data Collection	
Three case report forms will be used to collect essential data
 
Case Report Forms Include:
 
 1. Procedure Form 
 • Patient-specific details • Procedural and ablation data, including de-identified Carto case backup data • Complications/adverse events during the procedure 2. Complications/Adverse Events Form 
 • Adverse events that occur after the patient leaves the procedure room through discharge • Adverse events from the discharge date through 7 days post-procedure • Adverse events from day 8 through day 90 post-procedure 3. Effectiveness Form 
 • For patients with atrial fibrillation, follow-up will be performed at 1 month, 2 months, 3 months, 6 months, 9 months and 12 months post ablation. Patients' symptoms and 12-lead ECG will be recorded at each follow-up visit to assess recurrence, and a 7-day

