3 THE TRIAL

3.1 Trial design

This is a non-Inferior, Multi-Center, Prospective Randomized Controlled Trial ((1:1 randomization) conducted in China. The study aims to consecutively enroll up to 724 procedures over the course of one year at 10 EP centers with non-fluoroscopic labs accredited by the Chinese Heart Rhythm Society. The anticipated total study duration is 36 months, with a follow-up period of 12 months for each participant. The study will be completed after the last enrolled subject has finished the 12-month follow-up period.

Following informed consent, obtained either during the pre-procedure office visit or during hospitalization for the procedure, baseline data will be collected. This data will include patient demographics, medical history, prior treatments, and laboratory test results.

The initial enrollment ratio between PFA and RF was projected to be evenly distributed at 50% each. Peri-procedural data, including procedural details, ablation strategies, acute success rates, VISITAG parameters, and any complications or adverse events, will be recorded up to the patient's discharge.

Post-discharge, participants will undergo follow-up evaluations at 1,2, 3,6,9,12 months after the procedure. The follow-up schedule will remain unchanged even if a repeat ablation procedure is required.

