3.4.2 Secondary endpoints

[figure not shown]
- The acute success of the procedure.
- The proportion of intraoperative conversion to using X-ray.
- Utilization of lead personal protective equipment (PPE) and wear time.Well-being survey of staff.
- The proportion of patients with recurrence of targeted arrhythmia during the first 90 days post-ablation.
- Early recurrence of atrial arrhythmias, defined as any AF/AFL/AT episode lasting >30 seconds occurring during the blanking period.
- Late recurrence of atrial arrhythmias, defined as any documented AF/AFL/AT episode lasting >30 seconds occurring after the blanking period and up to 12 months.
- Impact of early recurrence on late recurrence, assessed through survival analysis and multivariable adjustment to evaluate whether early recurrence predicts subsequent late recurrence.
- AF burden, assessed by scheduled rhythm monitoring (e.g., 7-day Holter at 3, 6, 9, and 12 months), expressed as the proportion of time spent in AF during the monitoring period.
- Incidence of peri-procedural complication.
- Total procedure duration, ablation time.
- changes in quality-of-life (using the AF Effect on Quality of Life (AFQT) and the EuroQol Health-Related Quality-of-Life 3-Level (EQ-5D-3L)).

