7.5.4 SUSARs Reporting

Suspected Unexpected Serious Adverse Reactions [SUSARs] will undergo expedited reporting to relevant regulatory authorities (e.g., research ethics committees, National Medical Products Administration, and National Health

Commission of the People's Republic of China). Investigators must report all SUSARs to sponsor as soon as possible and 24h of learning of the event. These SUSARs will be centrally reviewed and reported by the sponsor as soon as possible:

For fatal or life-threatening SUSARs, sponsor must report as soon as possible and within 7 days of learning of the events. Active follow-up must be completed within the following 8 days (The first day of learning of the event is considered 0 day).

For fatal or life-threatening SUSARs, sponsor must report as soon as possible and within 15 days of learning of the events.

8. Statistical analysis

Continuous variables are expressed as mean \pm SD if normally distributed or median (interquartile range [IQR]) if not normally distributed. Intergroup differences will be compared by student's t-test (normally distributed data with equal variance) or Mann-Whitney U test (failed either normality or equal variance test). Categorical variables will be presented as percentages and compared by using the Chi-square test or Fisher's exact test. The Kaplan-Meier method will be used to describe event-free rates over time. The statistical significance for all tests will be accepted at $P < 0.05$.

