Appendix E. Well-being Questionnaire for Operating Room Staff

Basic Information

1. **Position:**

Lead operator Assistant Nurse Anesthesiologist Technician

2. **Procedure duration:** _____ hours _____ minutes

3. **Order of the case today:** No. _____

4. **Personal protective equipment (select all that apply):**

None Lead apron Lead cap Thyroid collar Lead skirt Lead glasses Dosimeter

1. Physical Discomfort and Pain Assessment

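### Staff well-being forms are clustered by procedure and by person, but the only group-comparison tests in Section 8 assume independent observations, so P values computed on individual forms can be too small

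*Protocol*

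**What the plan says.** The synopsis lists "Quality-of-life for staff at the end of each procedure" among the secondary endpoints. Section 3.4.2 lists it more briefly as "Well-being survey of staff", without timing or number of respondents. The instrument is Appendix E, the "Well-being Questionnaire for Operating Room Staff". Its position item offers "Lead operator Assistant Nurse Anesthesiologist Technician", and another item asks for "Order of the case today". The remaining items are graded scales (0–5, 0–4 and 0–10), ordered categories and yes/no answers. As shown, the form has no staff code, no case number and no summary score.

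The synopsis gives the volume as "Up to 724 patients (procedures) will be enrolled over 1 year at 16 EP centers"; Section 3.1 says the trial will "enroll up to 724 procedures over the course of one year at 10 EP centers".

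For continuous variables Section 8 says "Intergroup differences will be compared by student's t-test", or by the Mann-Whitney test where its assumptions fail. Categorical variables go to Chi-square or Fisher's exact test, and one significance threshold of 0.05 covers all tests. Section 8 does not mention the staff endpoint, a unit of analysis, or any method for clustered data.

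**The concern.** A form completed at the end of each procedure by people in several roles has two natural layers of dependence. Forms from one procedure share that case's length and difficulty. Forms from one person share that person's habits in scoring pain, fatigue and worry. The tests in Section 8 would count every form as a separate piece of information.

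Less need for heavy protective equipment is part of the background case for the non-fluoroscopic lab (Sections 1.1.2 and 1.1.4). A nominally significant staff result would be read as support for it. If the forms are correlated in the wrong way, that result could be a false positive far more often than one time in twenty. There is also a practical side: an analysis plan can add a model later, but it cannot recover a staff code that was never recorded.

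**Working it through.** The protocol gives no sample size or power for this endpoint, so there is no stated figure to reproduce. The question is how large the true type I error of a nominal 5% test becomes.

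**Inputs from the protocol.** 724 procedures; 16 centres (synopsis) or 10 (Section 3.1); five positions on the form; threshold 0.05. Procedures per centre: 724/16 = 45.25 or 724/10 = 72.4. At that volume, repeated answers from the same people are practically certain.

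**Inputs assumed.** Forms per procedure: 1 to 5. Within-procedure correlation: 0 to 0.3. Share of variance due to the staff member: 0 to 0.5. Staff-by-lab share: 0 or 0.1. Two staff per role per centre (per lab, if staff stay in one lab).

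**Formula.** Design effect DE = 1 + (m − 1) × ICC, where m is the number of correlated forms falling in the same arm. True type I error = 2 × [1 − Φ(1.96/√DE)].

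**Step 1: several forms per procedure.**
- m = 3, ICC 0.1: DE = 1.2, error 7.4%.
- m = 4, ICC 0.3: DE = 1.9, error 15.5%.
- m = 5, ICC 0.3: DE = 2.2, error 18.6%.

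Simulated t-tests (724 procedures, patient-level randomisation, 1,500 replicates, Monte Carlo error about 1 point) at a procedure share of 0.2 gave 9–10% with three forms and 14.5–15.7% with five. The formula gives 9.8% and 14.4%.

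**Step 2: same people repeatedly, working in both labs.** With a staff share of 0.3–0.5 and no procedure or staff-by-lab correlation, the simulated error was 3.8–5.9%. Each person's general level appears in both arms in roughly equal measure, so repetition alone does not inflate the error. One form per procedure from staff in both labs gave 4.0–5.5% when there was no staff-by-lab effect.

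**Step 3: staff-by-lab effect.** Forms now cluster by person within lab. With one form per procedure, the cluster size is 724/(16 × 2 × 2) = 11.3 or 724/(10 × 2 × 2) = 18.1. At a share of 0.1:
- 16 centres: DE = 1 + 10.3 × 0.1 = 2.03, error 17%.
- 10 centres: DE = 1 + 17.1 × 0.1 = 2.71, error 23%.

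Simulation, with one to five forms at 16 centres and one or three at 10, gave 18–26%. A procedure share of 0.1 was included. Five forms at 10 centres would be slightly above that: DE = 1 + 17.1 × 0.1 + 4 × 0.1 = 3.11, error about 27%.

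**Step 4: staff who work in one lab only.** The cluster sizes are the same, and the whole staff share now counts.
- 16 centres, share 0.3: DE = 1 + 10.3 × 0.3 = 4.09, error 33%.
- 10 centres, share 0.5: DE = 1 + 17.1 × 0.5 = 9.55, error 53%.

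Simulation gave 35–54%.

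**Step 5: would one mean score per procedure be enough?** With staff in both labs and only procedure-level correlation, a t-test on procedure means returned to 4.6–5.3%. It left 14–22% under staff-by-lab effects (three or five forms). With single-lab staff it left 28–46% (three or five forms, 16 centres).

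**The case against.** Section 8 is a general paragraph that never names this endpoint, and it is not a full list of analyses: the early-versus-late recurrence endpoint in Section 3.4.2 calls for multivariable adjustment that Section 8 does not mention. A clustered model for a staff survey could properly sit in a statistical analysis plan that is not at hand. The number of forms per procedure is not stated, staff rosters are not described, and no correlation is given. All of that stands, and it makes the size of the problem conditional.

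Two stronger readings should be resisted. One is that the P values for this endpoint are wrong. The protocol does not support that: step 2 shows the test near its nominal level when staff work in both labs with no procedure-level or staff-by-lab correlation, and a mean per procedure removes the within-procedure part. The other is that clustering could not be modelled later because the form lacks an identifier. Appendix E shows questionnaire content, not the database record. Appendix C, a patient instrument, also prints no ID field, whereas Appendix D does. Data go into an electronic system (Sections 4 and 6.1) that may link forms to cases.

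The objection does not remove the point. The only comparison tests the protocol states assume independence, several roles on a per-procedure form make multiple forms the natural reading, and no staff code is described anywhere in the protocol.

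**Conclusion.** The point holds in conditional form. Section 8's tests, applied to individual Appendix E forms, can give P values that are too small. The type I error is about 7–19% with three to five forms per procedure and a procedure correlation of 0.1–0.3, about 18–26% with a staff-by-lab share of 0.1, and about 35–54% if staff stay in one lab. It remains near 5% if staff work in both labs with no procedure-level or staff-by-lab correlation. Which case applies cannot be settled from the protocol, because forms per procedure, rosters and correlations are all assumed here. Only one secondary endpoint is affected; the primary endpoints are not. This is a cheap improvement.

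**What to change.** In Section 8, state that Appendix E scores are analysed with a mixed model: arm as fixed effect; random effects for staff member, staff-by-lab and procedure; adjustment for centre and staff role. Use an ordinal or logistic version for the graded and yes/no items. Equivalent cluster-robust standard errors would also serve. State how many staff are expected to complete a form per procedure.

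Record a coded staff ID and the case ID with each form, unless the database already holds them. This should not wait, since a staff code missing from completed forms may not be recoverable.

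The cost is a sentence or two in Section 8 and two coded fields. No patient procedure changes. The downside is that the forms become pseudonymous, and people in small teams could be recognised. Section 6.1 has the data analysed by the sponsor, so access to the key behind the staff code should be restricted.

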1.1 What is the problem to be addressed?

The problem to be addressed is whether the catheter ablation procedures for atrial fibrillation (AF) in a non-fluoroscopic electrophysiology (EP) lab have the same efficacy and safety to those procedures in a digital subtraction angiography (DSA) lab, especially when new techniques -like intracardiac echocardiography (ICE), contact force catheters, Pulse field ablation (PFA), etc.-could be used in both groups.

1.1.1 Catheter ablation of atrial fibrillation and guidelines

Catheter ablation has become a standard therapy for managing AF, particularly in patients with symptomatic paroxysmal or persistent AF who have failed medical therapy. Pulmonary vein isolation (PVI) remains the fundamental strategy for catheter ablation, and PVI is endorsed by guidelines from the European Society of Cardiology (ESC), American Heart Association (AHA), and Heart Rhythm Society (HRS) as the first-line approach for AF ablation^{1, 2}.

New innovations such as **contact force-sensing catheters**, **3D electroanatomic mapping systems**, and **ICE** have improved catheter positioning, lesion precision, and procedural safety. In addition, Recent technological advancements have further optimized the safety and efficacy of AF ablation. **PFA**, a novel non-thermal ablation modality, uses electroporation to selectively ablate myocardial tissue while sparing adjacent structures such as the esophagus, phrenic nerve, and pulmonary veins. PFA has demonstrated potential for shorter procedure times and reduced risks of complications, offering a promising alternative to conventional thermal ablation techniques³⁻⁶.

These advancements, combined with the established efficacy of PVI, are driving improvements in the outcomes and safety of catheter ablation procedures, addressing unmet needs in AF treatment, and broadening the scope of patients who can benefit from this therapy.

